[name] will serve as site PI. [name] will ensure that study participants are recruited in a timely and effective manner. She and her team will communicate regularly with the larger team regarding recruitment efforts and success for the Baylor College of Medicine (BCM) site. [name] research focuses on the complex nutritional and physiologic factors that impact pharmacokinetic and pharmacodynamic responses to dietary carotenoids. She and [name] will lead genetic analyses for Aim 2. [name] will serve on the Data Quality and Analysis and Genetic Analysis Teams. [name] is a clinical geneticist with research training in quantitative human genetics and will serve on the Genetic Analysis Team.

Objective

The purpose of Aim 2 is to define the RS-assessed skin carotenoid response (RS device sensitivity) compared to plasma carotenoid response during a 6-week randomized controlled trial intervention of a carotenoid-containing juice among 160 participants across four racial/ethnic groups. We hypothesize that there will be RS-assessed skin carotenoid increases after 6 weeks of daily consumption of carotenoid-containing juice for all racial groups, but the magnitude of RS-assessed skin carotenoid responses may differ between groups.

Experimental Questions

1. What is the skin carotenoid response to controlled carotenoid intake in a diverse cohort?
2. What are significant covariates related to the skin carotenoid response?

Background

Significance

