Pressure-mediated reflection spectroscopy offers an economical, commercially available, sensitive measure of skin carotenoids. Reflection spectroscopy (RS) (Figure 1) is an improved method over RRS for measuring skin carotenoid status.⁴⁶ To further explain the difference between RRS (previously published) and RS technology, the most important differences are that Reflection spectroscopy (RS) offers stronger signals, faster data acquisition, greater accuracy, control for melanin in the skin, and most importantly, portability (for field-based nutrition studies) in a commercially available device (Veggie Meter®, Longevity Link Corp.).^{17,18,46} RRS devices are not commercially available, and those that are available to researchers via a leasing agreement are not research grade. There are two custom-built RRS devices to our knowledge: One at Yale University and one at the USDA Grand Forks Human Nutrition Research Center. These devices are not portable and are not mass produced. There are other peer-reviewed papers examining "skin yellowness" using an instrument produced by Konica Minolta.^{47,48} The instrument works very differently from the RS device we propose to study, and measures "skin yellowness" through the "b" chromaticity coordinate. The Konica Minolta device is not designed for the measurement of carotenoid levels and does not correct for residual blood and melanin levels, so the error for carotenoid measurements is very high. Thus, there is a critical need to test the RS device to assess skin carotenoids in racially and ethnically diverse populations.

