To determine the sensitivity of the RS device for measuring change in fruit and vegetable (F&V) consumption in response to community-based nutrition interventions, we need to determine the longitudinal response to a defined F&V intervention. We want to learn if change in RS-measured skin carotenoids can be used to sensitively define F&V consumption changes across a range of consumption values. We would also like to determine if the RS device sensitivity differs by racial/ethnic group. Aim 2 will gauge what an increase in F&V intake would look like in terms of RS-assessed skin carotenoids in an ethnically and racially diverse population.

Study Setting

Participants will be recruited, enrolled, and measured from within the three intervention sites: 1) Greenville, North Carolina - East Carolina University (ECU), 2) Minneapolis, Minnesota - University of Minnesota (UMN), and 3) Houston, Texas - Baylor College of Medicine (BCM). At ECU, participant visits will take place at the East Carolina Diabetes and Obesity Institute facilities and the Department of Public Health Research (ECDOI) offices, located in the East Carolina Heart Institute. At UMN, participant visits will take place at the Epidemiology Clinical Research Center (ECRC) which is a part of the Division of Epidemiology and Community Health in the School of Public Health. At BCM, participant visits will take place at the Children's Nutrition Research Center Metabolic Research Unit (CNRC MRU).

Study Population, Eligibility, and Screening

Participants (n=160) will be recruited from the three intervention sites: ECU (n=60 participants), UMN (n=40 participants), and BCM (n=60 participants). As with Aim 1, participants will be recruited across four diverse groups: non-Hispanic African American/Black, Asian, non-Hispanic White, or Hispanic/Latinx. Though our power calculation found that a sample size of n=156 was needed, we chose to round up in order to easily and evenly divide participants by our three intervention sites. It is our intent to enroll approximately equal numbers of participants in each racial/ethnic group.

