Power calculations for Aim 2 are based off of Meinke et al.⁷⁰ which studied 30 adults (15 in the intervention group and 15 in the placebo control group) and used a dose of carotenoids (1.5 mg) most similar to the dose we are proposing. Based upon the data presented in Meinke et al. Figure 4, the standard deviation is 0.23 for 6-week relative skin carotenoid change. A sample size of 41 per group will have 90% power to detect 6-week relative skin carotenoids change of 1.13 vs. 1.28 when a one-sided two-sample t-test was used with a significance level of 0.05. With 20% attrition, we will need to enroll 52 per group, in each of three groups, for a total sample of 156.

Statistical Analysis

We hypothesize there will be RS-assessed skin carotenoid increases after 6 weeks of daily consumption of carotenoid-containing juice. To examine this hypothesis, we will compute changes in RS-assessed skin carotenoids from baseline to 3 weeks, from baseline to 6 weeks, and from 3 weeks to 6 weeks. Each level of change in RS-assessed skin carotenoids (as a response) will be analyzed using a general linear model to test the effects of carotenoid dose, melanin levels, and genetically determined ancestry, and dose x melanin and dose x genetically determined ancestry interactions. We will test baseline skin carotenoid level, baseline total plasma carotenoid level, baseline carotenoid intake and non-intervention carotenoid intake during the study, sex, age, skin hemoglobin index, blood total cholesterol, BMI status, body fat, season, and changes in self-reported total F&V intake in the model as potential covariates. If baseline confounding arises when the covariates differ significantly among the three intervention groups, a propensity score method will be adopted to balance the groups and control for the confounding. Similar analyses will be conducted when changes in plasma carotenoid are the response.

Plasma carotenoid analysis will be measured as described for Aim 1. We will also measure vitamin A status in the plasma as this can influence carotenoid absorption.

Interpretation

Upon successful completion of Aim 2, we will be able to translate RS intensity increases to an increase in F&V-derived carotenoid consumption. This will establish sensitivity of the RS device and enable better interpretation of findings from nutrition evaluation and surveillance studies using the RS device as an outcome measure.

Protection of Human Subjects

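### Dose by ancestry is tested only alongside dose by melanin, so the plan has no analysis of whether the device response differs by racial/ethnic group overall

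*Combined protocol and SAP*

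**What the plan says.** Statistical Considerations, Statistical Analysis: each change in the skin score "will be analyzed using a general linear model to test the effects of carotenoid dose, melanin levels". The same sentence then lists the remaining terms of that model: "genetically determined ancestry, and dose x melanin and dose x genetically determined ancestry interactions". One model is described. No version leaves out melanin and dose by melanin. The text does not say whether tests are partial or sequential, or which visit's melanin reading is used.

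The group question is put without a condition on pigment. The Objective hypothesizes that "the magnitude of RS-assessed skin carotenoid responses may differ between groups". Rationale/Strategy says "We would also like to determine if the RS device sensitivity differs by racial/ethnic group".

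The Significance section lists, among the advantages of reflection spectroscopy over resonance Raman spectroscopy, "control for melanin in the skin". Data Collection and Study Visits has melanin read on a separate spectrophotometer.

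The Power Calculation covers a two-group dose comparison only: "6-week relative skin carotenoids change of 1.13 vs. 1.28", with "the standard deviation is 0.23 for 6-week relative skin carotenoid change" and a "one-sided two-sample t-test was used with a significance level of 0.05". No power is given for dose by ancestry.

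**The concern.** The planned term and the stated question refer to different quantities. The question concerns the total difference in response between groups. The term is what remains of that difference after people of equal melanin are compared.

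Melanin can be expected to vary with ancestry, and pigment is a plausible route by which an optical device could respond differently. If that happened, the dose by ancestry term would tend toward zero although the groups did differ in practice. A field user carries the portable device and may have no melanin reading to adjust with, so the total difference is the one that user needs.

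At stake is the interpretation. A small or non-significant dose by ancestry term from this model would say little about whether sensitivity differs between groups as they are met in the field.

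**Working it through.** **1. The plan's own figure.** Difference 1.28 − 1.13 = 0.15, SD 0.23, one-sided 0.05, power 90%:

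n = 2 × (1.645 + 1.282)² × (0.23 / 0.15)² ≈ 40.3, so 41 per arm. Exact t-test power at 41 is 90.0%. With 20% attrition, 41 / 0.80 = 51.25, so 52 per arm and 3 × 52 = 156. This reproduces. It implies 3 × 41 = 123 completers, or 123 / 12 ≈ 10 per combination of four groups and three arms.

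**2. What the term estimates.** Let θ be the dose by group effect at equal melanin, δ the change in dose response per SD of melanin, and Δ the difference in mean melanin between two groups. Then:

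- without the melanin terms, dose by group estimates θ + δ × Δ;
- with melanin and dose by melanin in the model, it estimates θ.

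If the whole difference works through pigment, θ = 0 and the joint term has nothing to find. Sequential testing in the listed order gives the same result, because dose by melanin enters first.

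**3. Simulation.** From the plan: 123 completers, SD 0.23, mean high-dose rise 0.15, four equal groups, three arms. Assumed, because the documents give no figure:

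- R², the share of melanin variance lying between groups, from 0.3 to 0.8;
- a moderate-dose response half of the high-dose response;
- group melanin means;
- a pigment slope of 0.15 per melanin SD at high dose, or half of that.

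The test is a 6-df F-test at 0.05, with 2,000 trials per setting.

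*Difference carried wholly by pigment, slope 0.15 per SD: share of trials rejecting*

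| R² | Dose × group, no melanin terms | Dose × group, joint model | Dose × melanin, joint model |
|---|---|---|---|
| 0.3 | 17% | 5% | 54% |
| 0.5 | 27% | 5% | 40% |
| 0.7 | 40% | 5% | 27% |
| 0.8 | 45% | 5% | 20% |

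At half the slope, dose by group without the melanin terms rejects in 7%, 9%, 12% and 13%, against 5% in the joint model. At R² 0.7 and the full slope, the mean high-dose contrast between the extreme groups is −0.36 without the melanin terms and 0.00 with them. The −0.36 corresponds to groups 0.36 / 0.15 = 2.4 melanin SDs apart.

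*Direct difference, not through pigment (extreme-group contrast −0.425 at high dose)*

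| R² | No melanin terms | Joint model |
|---|---|---|
| 0.3 | 57% | 39% |
| 0.5 | 57% | 28% |
| 0.7 | 57% | 17% |
| 0.8 | 57% | 13% |

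Here the joint estimate is unbiased but less precise. At R² 0.7 its standard deviation is 0.279, against 0.147 without the melanin terms.

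A separate simulation on the same plan inputs gave 15% to 42% against about 5% for the full-slope pigment case, about 8% at the low end of the half-slope case, and a fall from 54% to between 37% and 11% for the direct case.

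**4. Melanin measured with error.** With reliability 0.8, R² 0.7 and the full slope, removal is partial. The contrast is −0.16 in the joint model against −0.35 without the melanin terms, and rejection is 7% against 37%.

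**5. Precision of the melanin-free contrast.** The difference between two groups in high-dose minus control response has a standard error of about 0.23 × √(4 / 10.25) = 0.144. A 95% interval is then about ±1.96 × 0.144 = ±0.28, which is wider than the 0.15 the trial is designed to detect.

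**The case against.** **The pigment effect is tested in the same model.** This stands. A response that falls with pigment appears in dose by melanin, and at R² 0.3 or 0.5 that test is more powerful than dose by group without the melanin terms (54% against 17%, and 40% against 27%). A reader might infer that the effect is lost from the study. It is not; it appears under another term. That term still does not say how far apart the groups are.

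**Separating pigment from ancestry serves a purpose.** This also stands. The Background stresses the limits of self-reported race, and the second experimental question asks for covariates of response. The joint model is a sound analysis of why groups differ.

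**The device is said to correct for melanin.** If the correction is complete, there is no pigment effect to remove and only the loss of power remains. The plan's own dose by melanin term shows that the sponsor means to examine this.

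**The group comparison is not what the trial is powered for.** Correct. The hypothesis restated in the analysis section is a rise with carotenoid juice, and the group question is worded more softly. It remains a stated question, and the plan names no analysis that answers it.

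**The sizes rest on assumptions.** They do. The full slope equals the whole mean effect: at high dose, a person one melanin SD above average would show a rise of 0.15 × (1 − 1) = 0. Half that slope gives much smaller rejection rates. If ancestry enters as continuous admixture proportions, the degrees of freedom and power will differ from a four-group model.

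**Conclusion.** The mismatch holds and follows from the model text. The only dose by ancestry test is conditional on melanin, while the question is not. Complete removal of a pigment-carried difference requires that the effect be linear in melanin and that melanin be measured without error; otherwise removal is partial. The percentages depend on the assumed R², slope and group means, and should be read as ranges.

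Three stronger readings are tempting, and the documents do not support them:

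- That the sponsor will report equal sensitivity from a null dose by ancestry term. No section says so; it is a risk of interpretation.
- That the melanin-free test would settle the question. On the plan's effect size it rejects in only about 7% to 45% of trials in the pigment settings, so a null there is also weak evidence.
- That its power is much higher, from applying 0.15 to each dose step. That makes the high-dose rise 2 × 0.15 = 0.30, whereas the plan gives 0.15 as a single two-group difference.

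**What to change.** 1. Name dose by group, without melanin or dose by melanin, as the analysis of whether sensitivity differs by group. State whether group means self-identified race/ethnicity or genetic ancestry. Report group-specific dose responses and their differences with confidence intervals.
2. Keep the planned joint model as a second step that shows how much of any group difference pigment explains. Read its dose by ancestry and dose by melanin terms together. State which visit's melanin value is used and whether tests are partial or sequential.
3. State that a null dose by group term in either step is not evidence of equal sensitivity, because the trial is powered only for the dose comparison.

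The cost is a short addition to the analysis text and one extra model fit per outcome. No new data are needed.

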A small amount of blood collected for each participant will be stored temporarily at each of the three intervention sites (ECU, UMN, and BCM) while data collection occurs. After data collection is complete, this small amount of blood will be sent and stored/banked indefinitely at ECU to be used for future analysis/research. Participant information and privacy will be protected by using a unique ID to label

participant samples and other information. This ID will be kept securely and separately from other participant identifying information. Participants will be given the choice of opting to bank their samples or not on the consent form.

Safety Considerations

Data and Safety Monitoring Plan

This goal of Aim 2 is to examine sensitivity of RS-assessed skin carotenoid status as a marker of fruit and vegetable consumption in a racially and ethnically diverse sample of individuals. We will use data from Aim 2 (along with data from Aim 1) to provide predictive algorithms for interpretation.

The intervention and measurement protocols associated with this proposed study pose minimal risk to participants. Because of the low risk status, the Data Safety Monitoring Plan (DSMP) for this proposed study focuses on close monitoring by the Principal Investigator as well as the Safety Officer. We will promptly report excessive Adverse Events (AE) as well as any Serious Adverse Events (SAE) to the IRB at East Carolina University and to NHLBI by following the necessary protocols established by those institutions. Safety reports will also be created for the Safety Officer as part of the DSMP and will reflect the following: 1) recruitment and retention rates, 2) compliance for juice intervention subjects, 3) Adverse Events, and 4) Serious Adverse Events and other situations that might be of safety concern. Safety reports will be compiled by the Study Coordinator and sent to the Principal Investigator and Safety Officer. The frequency of data review for this study will be dependent on the type of data and is summarized in the following table.

Data Type	Frequency of Review
Participant Recruitment Rate	Monthly during recruitment of participants.
Participant Retention Rate	Monthly during the juice intervention beginning with the week 3 data collection period.
Juice Intervention Compliance	Monthly during the 6-week intervention.
Safety Report & Adverse Events	Every 6 months (safety report) and within 72 hours of being notified of an event (AE).

- Participant Recruitment Rate: Reflects the description of recruitment efforts and demographic characteristics (sex and race) for Aim 2. This will be especially important to track as we plan to recruit and enroll approximately equal numbers of participants in each racial/ethnic group for Aim 2.
- Participant Retention Rate: Reflects the summary of retention efforts and participant numbers by wave of participants for Aim 2. This will be reported monthly for Aim 2.
- Intervention Compliance: Description of text messages, phone calls, and completed juice logs at 3- and 6-week follow up. This will be reported monthly during the juice intervention.

Safety Report: AE (injuries) and SAE (if they are severe enough to be classified as an SAE) will be documented and reported in a safety report format and provided every 6 months. All protocols for reporting SAE to the necessary institutions within the appropriate timeframe will be followed. In addition, AE will be documented within 72 hours of being notified of the event and shared with the Safety Officer to determine if they qualify as an SAE.

Qualifications and Responsibilities of the Safety Officer

The Safety Officer for this study is [name], MD, PhD, FAAP, Department of Pediatrics and Center for Health Disparities Director: Pediatric Healthy Weight Research and Treatment Center and Associate Director of the Integrative Health Sciences Facility Core NCSU Center for Human Health and the Environment at ECU. [name] will address any questions with clinical implications. He has previously served as Safety Officer on a study of similar nature and design, so he is the ideal person to serve in this role. As the Safety Officer, [name] will review the reports sent by the Study Coordinator (at the frequency described in the table above) and will determine whether there is need for a corrective action that should be communicated to the study Principal Investigator, the ECU IRB, and NHLBI. This review by [name] will ensure adherence to safety protocols and achievement of recruitment and retention rates commensurate with our aims.

Measurement and Reporting of Adverse Events

We do not expect any AE as a result of participating in this study. However, if any AE occur study staff will report them using the AE section within the ECU IRB website. The Safety Officer will review and evaluate AE within 72 hours of being notified of the event by study staff. Any study-related SAE will be reported to NHLBI within the timeline set forth by the institute. A safety report containing AE, SAE, and their rates of occurrence will be generated every 6 months and reviewed by the Safety Officer at that time.

- Measurement and reporting of participant compliance to treatment protocol: Once participants who have been randomized to the intervention treatment group have started the juice intervention, compliance will be reviewed monthly by the Principal Investigator and Safety Officer. If compliance in the juice intervention becomes an issue, we will re-evaluate our compliance plan to improve compliance.
- There is a modest risk of weight gain for Aim 2 participants who will be provided with carotenoid-containing or apple juice. The juices provide 60 and 90 kcal/6 fl. oz, respectively. We will provide education on the additional energy provided and dietary strategies to adjust their caloric intake as to remain isocaloric. If we see a >5% increase in body weight at the week 3 timepoint, we will provide additional dietary education to the subjects.
- Measurement of retention status: For the Aim 2 juice intervention, we will collect measures similar to Aim 1 at baseline, 3 weeks, and 6 weeks after the participants are randomized to a control group (negligible-dose carotenoids), a moderate-dose carotenoids group, or a high-dose carotenoid group. Our goal is to retain at least 85% of our initial sample, though we have powered our study to accommodate a more conservative retention rate (80%). We will review the rate of subject accrual monthly during the initial enrollment period and dropout rates on a quarterly basis. We will make regular contact with participants to encourage continued participation.
- Stopping rules: In this minimal risk study to determine the sensitivity of the RS device (the Veggie Meter®), it is very unlikely that an event would occur that would require stopping the trial. However, as previously described, we will monitor injury rates of all participants. The Safety Officer, together with the study investigators, will alert the IRB at East Carolina University and NHLBI if a larger than reasonably expected injury rate should occur among participants in the intervention condition.

COVID-19 Safety Plan

Research staff at each of the intervention sites will follow their home University's approved/required COVID-19 screening plan. Participant COVID-19 screening will occur via phone the evening before the participant's study visit and again upon arrival to the visit the following day. This process will occur at each of the three participant visits.

In addition to participant COVID-19 screening questions, each site has and will follow site-specific requirements for study/clinic/lab spaces. Common requirements across all three sites includes:

- Staff will be required to wear various levels of personal protective equipment (PPE) such as masks, gloves, and face masks
- Participants will be required to wear face masks
- Staff and participants should maintain a distance of 6 ft whenever possible during the study visit
- Staff will clean common surfaces (e.g., tables and chairs, pens/pencils/stylus, light switches, doorknobs/handles) and equipment (e.g., the Veggie Meter® device, the Konica Minolta device, scale/height board, TANITA scale, iPads/computers, computer mouse/touchpads) before and after each participant's visit.

References

